#### 5.3. Analysis of the Primary Endpoint

The primary analysis will include all randomized subjects from the BMT CTN 0702 protocol, classified according to their randomized treatment allocation, irrespective of treatment actually received [intent-to-treat]. The time to this event is the time from randomization on the BMT CTN 0702 protocol to progression, initiation of non-protocol anti-myeloma therapy, or death from any cause. Patients will be censored at loss to follow-up or end of 2018, whichever comes first. Deaths without progression are treated as failures no matter when they occur. The analysis will be conducted once all living patients have been followed for 5-years post randomization on the BMT CTN 0702 protocol.

Data for patients not enrolled on the long-term follow-up protocol will be included from the BMT CTN 0702 protocol. Additionally, patients who do not consent to the long-term follow-up or who have progressed on the BMT CTN 0702 protocol will be followed according to the standard CIBMTR long-term follow-up mechanism. The treatment arms will be compared with a two-sided log-rank test stratified on risk status. Tests will be performed pair-wise at the .01667 level in order to maintain study-wide type I error at 0.05. PFS will be compared between treatment arms as a time to event analysis. A secondary analysis of PFS will be conducted using Cox regression, adjusting for demographic and baseline characteristics which are statistically

different between treatment arms ( $p < 0.1$ ). Additionally, discontinuation of lenalidomide maintenance will be considered as a time-varying covariate in the Cox regression model.

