1.1.1 Primary Objective

The primary objective of the study is to compare progression-free survival (PFS) as a time to event analysis between the three randomized treatment arms from the BMT CTN 0702 protocol as a pairwise comparison. The analysis will be conducted once all alive patients have been enrolled for 5 years post randomization on the BMT CNT 0702 protocol.

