1.2 Study Design and Procedures

1.2.1 Primary Hypothesis and Primary Endpoint

The primary hypothesis of this study and the original BMT CTN 0702 study is that the use of novel anti-myeloma agents will improve long-term PFS after high-dose melphalan followed by autologous hematopoietic cell transplantation (HCT) as compared to a second autologous transplantation.

To correspond with the primary objective to compare progression-free survival (PFS) as a time to event analysis between the three randomized treatment arms from the BMT CTN 0702

protocol as a pairwise comparison, the main null and alternative hypotheses of the study are that the different treatment arms will have different rates of long-term PFS:

H₀₁: PFS_{Auto/Auto} = PFS_{Auto/RVD}
H_{A1}: PFS_{Auto/Auto} ≠ PFS_{Auto/RVD}

H₀₁: PFS_{Auto/Auto} = PFS_{Auto/Maint}
H_{A1}: PFS_{Auto/Auto} ≠ PFS_{Auto/Maint}

Ho1: PFSAuto/RVD = PFSAuto/ Maint Ha1: PFSAuto/RVD ≠ PFSAuto/ Maint

These three hypotheses will each be tested with a two-sided stratified log rank test at the α =0.05 / 3 level using a Bonferroni correction to control the overall type I error rate.

The primary endpoint is PFS. Patients are considered a failure of the primary endpoint if they die or suffer from disease progression. The time to this event is the time from randomization on the BMT CTN 0702 protocol until progression, death, or initiation of non-protocol anti-myeloma therapy, or until last myeloma follow-up through December 2018 if there is no event.

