2.1 Sample Size and Power Calculations

The projected sample size for this study was determined from the available sample size of the parent study, BMT CTN 0702, and the rate of progression-free survival on 0702. Seven hundred and fifty-eight participants enrolled on 0702, and it was anticipated that the sample size on 07LT could range from 417 to 569 for 3-year PFS ranging from 55% to 75%.

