2.3 Multiple Comparisons

All tests for treatment group differences that compare 2 groups at a time will be compared at the 0.05/3 significance level to adjust for the pairwise testing. Kaplan Meier estimates, cumulative incidence estimates, and hazard ratios for treatment groups will be presented with 98.3% confidence limits.

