4.1 Analysis of the Primary Endpoint

The primary analysis of PFS will include all randomized subjects from the BMT CTN 0702 protocol, classified according to their randomized treatment allocation, irrespective of treatment received [intent-to-treat]. The time to this event is the time from randomization on the BMT CTN 0702 protocol to progression, initiation of non-protocol anti-myeloma therapy (this includes lenalidomide if the dose is above 15mg), or death from any cause reported on BMT CTN 0702, BMT CTN 07LT, or to the CIBMTR. Patients will be censored at loss to follow-up or end of 2018, whichever comes first. For those lost to follow-up, if loss occurred during 0702, censoring will occur at last myeloma evaluation before loss to follow-up. For those lost to follow-up on BMT CTN 07LT, censoring will occur at the last contact date reported on the study status follow-up form. For those who completed BMT CTN 0702 but did not enroll on 07LT, censoring will occur at the last evaluation of progression provided by the CIBMTR.

The treatment arms will be compared with a two-sided log-rank test stratified on risk status. Tests will be performed pair-wise at the 0.05/3 level to maintain type I error at 0.05 for this endpoint in this analysis. A Kaplan-Meier plot of PFS and 5-year estimates of PFS will be provided by treatment group.

A secondary analysis of PFS will be conducted using Cox regression, with treatment arm and risk strata as covariates, and adjusting for demographic and baseline characteristics which are statistically different between treatment arms (p<0.1) for covariates specified in section 3.1. Start time will be randomization on BMT CTN 0702.

In another secondary analysis of PFS, discontinuation of lenalidomide maintenance will be considered as a time-varying covariate in a separate Cox regression model for those who initiated lenalidomide; in this model, the outcome will be the time to progression or death from initiation of lenalidomide. Initiation of maintenance lenalidomide on BMT CTN 0702 will be the start time for this analysis. CIBMTR data will be used to determine whether participants who discontinued study lenalidomide also discontinued commercial lenalidomide. The limited interpretation will be noted for this analysis, since it will include non-randomized comparisons and there may be bias in who enrolled in BMT CTN 07LT.

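### Fixed 0.05/3 for all three pairwise PFS tests is valid, but Shaffer's step-down keeps the same 0.05 bound and gains power on the second and third comparisons

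*SAP*

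**What the plan says.** The primary objective (SAP 1.1.1) is to compare PFS "between the three randomized treatment arms from the BMT CTN 0702 protocol as a pairwise comparison". SAP 1.2.1 lists all three null hypotheses: Auto/Auto equals Auto/RVD, Auto/Auto equals Auto/Maint, and Auto/RVD equals Auto/Maint. Each is tested at 0.05/3, "using a Bonferroni correction to control the overall type I error rate". On the test itself SAP 4.1 says: "The treatment arms will be compared with a two-sided log-rank test stratified on risk status". On its level the same section says: "Tests will be performed pair-wise at the 0.05/3 level to maintain type I error at 0.05".

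The level is the same wherever it appears. Protocol 5.3 states: "Tests will be performed pair-wise at the .01667 level in order to maintain study-wide type I error at 0.05". SAP 2.3 states: "All tests for treatment group differences that compare 2 groups at a time will be compared at the 0.05/3 significance level". The opening bullets of SAP section 2 and the footnotes of the treatment-comparison exhibits repeat 0.05/3. SAP 2.3 adds that Kaplan-Meier estimates, cumulative incidence estimates and treatment hazard ratios "will be presented with 98.3% confidence limits".

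Neither document describes a step-down rule, a closed test or an order of testing. Neither gives a hazard ratio, an event target or a power figure for PFS.

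**The concern.** Bonferroni treats the three hypotheses as if any combination of them could be true. Three pairwise equalities among three arms cannot behave that way. If A equals B and B equals C, then A equals C, so the number of true nulls is 3, 1 or 0 and never exactly 2. After one correct rejection, guarding against two further true nulls is protection against something that cannot happen.

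What is at stake is the ability to say more than that some pair of arms differs. The stated hypothesis sets novel agents against a second transplant, so a result in which one arm stands apart from the other two is a natural possibility. Describing it fully needs two rejections, and the fixed threshold makes the second harder to reach than error control requires. The randomized cohort is closed ("Seven hundred and fifty-eight participants enrolled on 0702", SAP 2.1), so a more efficient rule is a nearly free gain.

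**Working it through.** **The plan's own figures.** 0.05/3 = 0.01667, the level in protocol 5.3. Three tests at that level sum to 0.05. 1 - 0.05/3 = 98.33%, the stated confidence level. The figures 417 and 569 in SAP 2.1 are 758 x 0.55 = 416.9 and 758 x 0.75 = 568.5. They project enrolment and are not power calculations. There is no power figure to reproduce.

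**The step-down rule.** Order the three p-values. Test the smallest at 0.05/3. If it is rejected, test each of the other two at 0.05; otherwise stop.

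**Why the 0.05 bound holds.**
- Three true nulls: a false rejection requires the smallest p-value to fall below 0.05/3. This is the same event as under Bonferroni, so the probability is at most 3 x 0.05/3 = 0.05.
- One true null: it is never tested above 0.05, so the probability of rejecting it is at most 0.05.
- No true null: no false rejection is possible.

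Each pairwise log-rank test uses only its own two arms, so its level does not depend on the third arm. Everything Bonferroni rejects is also rejected here. None of this depends on an assumed effect size.

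**Size, on assumed inputs.** Assume 125 events per arm (375 of 758, about 49%) and one arm at HR 0.75 against two equal arms.
- Standard error of the log hazard ratio: sqrt(1/125 + 1/125) = sqrt(0.016) = 0.1265.
- Expected z: |ln 0.75| / 0.1265 = 0.2877 / 0.1265 = 2.274.
- Power at 0.05/3 (critical value 2.394): Phi(2.274 - 2.394) = Phi(-0.120) = 45.2%.
- Power of one test run alone at 0.05 (critical value 1.960): Phi(0.314) = 62.3%. This is the ceiling for any gain on a single comparison.

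The step-down lies between these, and its value needs the joint distribution of the three statistics. A simulation of 1,000,000 draws of three arm log-hazards with variance 1/events gives:

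| HR 0.75, 125 events per arm | Bonferroni | Step-down |
|---|---|---|
| Power per false null | 45.2% | 52.5% |
| Power to reject both false nulls | 28.6% | 43.1% |
| At least one rejection | 61.9% | 61.9% |
| Rejection of the one true null | 1.7% | about 4.5% |

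Other inputs:
- HR 0.70, 125 events per arm: per comparison 66.5% to 74.2%; both 51.5% to 66.8%.
- HR 0.75, 100 events per arm: per comparison 36.0% to 42.4%. With 150 events: 53.9% to 61.6%.
- One arm better, HR 0.60 to 0.80 and 40% to 60% of patients with an event: gain of about 1 to 9 points per comparison and 2 to 16 points for finding both.
- Graded arms, the third midway on the log scale, same ranges: about 0 to 2 points on the largest contrast and 3 to 17 points on each intermediate one.
- All three arms equal: familywise error 4.4% under both rules. One arm very different: the step-down's error for the one true null approaches 5.0%, against 1.7% for Bonferroni.

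**The case against.** The strongest reply is that nothing is broken. Bonferroni controls the error it claims to control, the protocol and SAP agree on it, and each 0.05/3 test matches a 98.3% hazard-ratio interval. A single-step rule with matching intervals is a legitimate choice. All of that stands, so this is an efficiency suggestion.

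A reader might infer more than the documents support:
- **That the trial has less chance of finding any PFS difference.** It does not. The first step is also 0.05/3, so the probability of at least one rejection is identical.
- **That the gain costs no type I error.** Only the 0.05 bound is shared. When exactly one null is true, the actual error rises from 1.7% towards 5%.
- **That a better test is the only route to more power.** Log-rank power depends on events, and this protocol exists to add follow-up. SAP 4.1 also plans a covariate-adjusted Cox analysis.
- **That one arm differing from two equal arms is the planned alternative.** The hypothesis favours novel agents over a second transplant but does not say the other arms are equal, and the SAP lists three symmetric two-sided nulls. With graded arms the largest contrast gains almost nothing.

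Two practical objections also stand. A comparison with p between 0.0167 and 0.05 could be declared significant while its 98.3% interval includes no difference. And SAP 2.4 says these endpoints were already tested on 0702, without adjustment here, so relaxing later thresholds once the ranking of arms may be known could look data-driven. The first needs a footnote; the second makes timing and documentation essential.

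**Conclusion.** The point holds as an efficiency improvement. The planned rule is valid, and the step-down dominates it at the same 0.05 familywise bound; that result rests on logic alone. The benefit is confined to the second and third comparisons: under the main assumed scenario about 7 points per comparison (52.5 - 45.2 = 7.3) and 14 to 15 points for finding both differences (43.1 - 28.6 = 14.5). These sizes depend on hazard ratios and event counts that the documents do not give. The cost is a higher, still controlled, error for a single true null and looser agreement between test and interval. The change is worth making if it can be fixed before 07LT results by arm are seen. If it cannot, the existing rule should stand.

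**What to change.** Before any 07LT outcome comparison by arm is seen, replace the fixed level with this rule: order the three stratified log-rank p-values; test the smallest at 0.05/3; if it is rejected, test each of the other two at 0.05; otherwise stop.

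- Make the change together in protocol 5.3, SAP 1.2.1, section 2, 2.3 and 4.1, and the exhibit footnotes that cite 0.05/3. Editing only some of these would make the documents contradict each other. For the Cox exhibits, state whether the treatment contrasts follow the rule or stay at 0.05/3.
- Record the departure, with its date and reason, in SAP 2.8.1.
- The same rule may be applied within each of OS, EFS and SPM, since the logical link between the equalities is the same. The power figures above are for PFS-type assumptions and do not carry over.
- Keep the 98.3% limits, with the three treatment hazard-ratio intervals labelled as simultaneous. Add a footnote that a comparison rejected at the second step may have a 98.3% interval that includes no difference.

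The cost is a protocol and SAP wording change and the loss of exact test-interval agreement at the second step. No new patients, data or assumptions are needed.

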1.5 Response Variables and Data Collection Time Points

Participants are evaluated for the primary endpoint of progression-free survival (death, disease progression, initiation of non-protocol myeloma therapy) and for the following secondary endpoints:

- Overall survival
- Event-free survival (no progression, death, or SPM)
- Incidence of SPM
- Unexpected grades 3-5 adverse events
- Health quality of life

Patients have visits every six months until death, progression, withdrawal of consent, or the end of the study.

Participants who receive long-term lenalidomide maintenance therapy are required to report unexpected grades 3-5 adverse events until the patient progresses or until 28 days from their last dose of lenalidomide. These require expedited reporting within 24 hours – 3 business days of the site's knowledge of the event, depending on the type of event. The protocol specifies additional rules for reporting requirements of AEs after an SPM depending on the treatment received for the SPM, and for reporting serious expected adverse events and selected AEs of interest.

Participants who do not receive lenalidomide maintenance or have permanently discontinued lenalidomide maintenance not required to report adverse events except for SPMs.

For all participants on 07LT, SPMs must be reported within three business days of knowledge of the event and deaths must be reported within 24 hours of knowledge of the participant's death. Non-melanoma skin cancers are not required to be reported.

Health quality of life surveys are completed at visits corresponding to 5, 6, and 7 years from original randomization on 0702.

2. General Statistical Considerations

Unless stated otherwise:

- For continuous outcomes, descriptive statistics will include the number of subjects (n), mean, standard deviation, median, minimum and maximum.
- For categorical outcomes, frequencies and percentages will be displayed for categorical data.
- All statistical comparisons made using 2-sided pairwise tests will be compared to an α =0.05/3 significance level.

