Exhibit 07LT-4B: Multivariate Cox Regression Analysis of Progression-free Survival from Initiation of Lenalidomide (Secondary Analysis of PFS)

Maximum Likelihood Estimates and Hazard Ratios

		0		
Covariate	Point Estimate	Lower Confidence Limit	Upper Confidence Limit	Model Parameter Estimate p-value
Auto/Auto treatment arm vs Auto/Maintenance arm¹				
Auto/Auto treatment arm vs Auto/RVD arm ¹				
Auto/RVD treatment arm vs Auto/Maintenance arm ¹				
Risk strata—High risk vs Risk strata—Standard risk				
Permanent discontinuation of lenalidomide (time-dependent)				
(other adjustment factor as needed)				
(other adjustment factor as needed)				
(other adjustment factor as needed)				

¹ P-values are compared to the 0.05/3 significance level.

Figure: A forest plot for the hazard ratios and confidence intervals may also be provided.

Notes for this secondary analysis:

Model covariates:

[figure not shown]
- Treatment group
- Randomized risk strata
- Any of the factors in column 2 of the table in Section 3.1 that have a test for treatment group differences that is significant at the 0.1 level. ERC-adjudicated baseline disease response will be tested using 2 categorizations (CR or better, VGPR or better). If both are significant at the 0.1 level, the one that is more significant will be used in the model.
- No interactions
- Permanent discontinuation of lenalidomide as a time varying covariate.

- Analysis population is 0702 participants who initiated lenalidomide
- Time to PFS is calculated from start time of lenalidomide
- Proc phreg in SAS, no model selection procedure

Exhibit 07LT-5: Overall Survival

Figure template for illustration only

Overall Survival by Treatment Arm

Kaplan Meier Estimates and 98.3% Confidence Intervals

	Auto/Auto	Auto/RVD	Auto/Maint		
5-year Estimates:	XX.X (XX.X, XX.X)	XX.X (XX.X, XX.X)	XX.X (XX.X, XX.X)		

Stratified Log-Rank Test for Treatment Group Differences

[figure not shown]
Treatment Group Comparison	p-value ¹
Auto/Auto vs Auto/RVD	0.XX
Auto/Auto vs Auto/Maint	0.XX
Auto/RVD vs Auto/Maint	0.XX

¹Significance level is 0.05/3 for each pairwise comparison.

Exhibit 07LT-6: Event-Free Survival

Figure template for illustration only

Event-Free Survival by Treatment Arm

Kaplan Meier Estimates and 98.3% Confidence Intervals

	Auto/Auto	Auto/RVD	Auto/Maint		
5-year Estimates:	XX.X (XX.X, XX.X)	XX.X (XX.X, XX.X)	XX.X (XX.X, XX.X)		

Stratified Log-Rank Test for Treatment Group Differences

[figure not shown]

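### The lenalidomide-discontinuation Cox model is labelled an analysis of PFS, but its stated outcome omits non-protocol anti-myeloma therapy, so read literally its hazard ratio is not for PFS as the plan defines it

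*SAP*

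**What the plan says.** SAP 4.1 defines the primary PFS event as progression, "initiation of non-protocol anti-myeloma therapy (this includes lenalidomide if the dose is above 15mg), or death from any cause". SAP 1.5 gives the same three components: "progression-free survival (death, disease progression, initiation of non-protocol myeloma therapy". Protocol 5.3 and the footnotes to Exhibit 07LT-3 agree.

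Later in SAP 4.1 the discontinuation model is introduced: "In another secondary analysis of PFS, discontinuation of lenalidomide maintenance will be considered as a time-varying covariate". It is fitted in those who initiated lenalidomide, and "in this model, the outcome will be the time to progression or death from initiation of lenalidomide". The notes to Exhibit 07LT-4B do not repeat an event list. They say only "Time to PFS is calculated from start time of lenalidomide".

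The plan promises to note the limited interpretation of this model, citing non-randomized comparisons and possible bias in who enrolled on 07LT. Non-protocol therapy is not mentioned there.

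**The concern.** One SAP section supports two event variables for an analysis carrying one name. A programmer who follows the model's own sentence would count progression or death only. A programmer who follows the exhibit would use the PFS variable.

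The choice matters more here than in an ordinary PFS model, because the omitted event is linked to the covariate. Moving to another regimen usually means stopping lenalidomide. Under the literal sentence that patient is still at risk, coded as discontinued, and any later progression on the next regimen counts towards the effect of stopping maintenance. In the other direction, a patient whose lenalidomide goes above 15 mg is a failure in the primary analysis but could still be at risk here as on lenalidomide.

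What is at stake is the meaning of the discontinuation hazard ratio in Exhibit 07LT-4B.

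**Working it through.** **1. The plan's own figures.** The documents give no event count, power, discontinuation rate or non-protocol-therapy rate for this model, so none can be reproduced. The related figures do reproduce: 758 × 0.55 = 416.9, giving 417; 758 × 0.75 = 568.5, giving 569; 0.05/3 = 0.01667. The 3-year PFS range of 55% to 75% is used below to set a baseline hazard.

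**2. The event set, place by place.**

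| Place | Non-protocol therapy an event? |
|---|---|
| Protocol 5.3, PFS | Yes; discontinuation enters the PFS Cox model with no narrower outcome |
| SAP 1.2.1 | Yes; one sentence has two components, the next adds it |
| SAP 1.5 | Yes |
| SAP 4.1, primary analysis | Yes, including lenalidomide above 15 mg |
| Exhibit 07LT-3 | Yes |
| SAP 4.1, discontinuation model | **No** |
| Exhibit 07LT-4B | Not stated; outcome called PFS |
| SAP 2.8.1, changes | No change of outcome listed |
| SAP 4.3, EFS model from lenalidomide initiation | **No**; second primary malignancy is also missing |

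**3. Who stays at risk under the literal sentence.** SAP 2.2 censors a participant without an event when data for the endpoint stop being available. Starting another therapy does not stop the data: patients who stop lenalidomide remain in follow-up (Protocol 2.4.1, SAP 1.4), visits run until death, progression, withdrawal or study end (Protocol 4.2.1), and CIBMTR data supplement PFS (SAP 2.2). Nothing censors at non-protocol therapy, so by default these patients stay in the risk set.

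**4. What that does to the hazard ratio.** Let *h* be the progression/death hazard, unchanged by stopping (true ratio 1.0). Let *n_on* and *n_off* be the rates of starting non-protocol therapy on and off lenalidomide, *k* the multiplier on *h* afterwards, and *s* the share of discontinued person-time that falls after non-protocol therapy. Every start of non-protocol therapy is taken to end lenalidomide, so the above-15-mg case is not modelled.

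- Ignored (literal text): ratio ≈ 1 + *s*(*k* − 1).
- Counted as an event, with direct switches charged to the on-lenalidomide state: ratio = (*h* + *n_off*)/(*h* + *n_on*).
- Censored: ratio = *h*/*h* = 1.

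Here *h* = −ln(0.55)/3 = 0.1993 or −ln(0.75)/3 = 0.0959 per year. Assumed: stopping 0.15/yr, 5 years of follow-up, *k* = 0.5, 1 or 2. Results are from a time-dependent Cox model on 400,000 simulated patients per scenario.

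| 3-yr PFS | n_on, n_off | Ignored, k = 0.5 / 1 / 2 | Event | Censored |
|---|---|---|---|---|
| 55% | 0.01, 0.05 | 0.93 / 1.00 / 1.11 | 1.19–1.20 | 1.00–1.01 |
| 55% | 0.02, 0.20 | 0.83 / 1.00 / 1.28 | 1.82–1.83 | 1.01 |
| 75% | 0.01, 0.05 | 0.93 / 1.00 / 1.11 | 1.37–1.38 | 0.99–1.00 |
| 75% | 0.02, 0.20 | 0.82 / 1.00 / 1.30 | 2.54–2.56 | 0.99–1.00 |

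Hand check of row 1: *s* = 15% at *k* = 0.5 gives 1 + 0.15 × (−0.5) = 0.925; event, 0.2493/0.2093 = 1.19. Across the rows about 6% to 21% of initiators start non-protocol therapy before progression.

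**5. When counting it as an event returns 1.0.** Take *h* = 0.12, stopping 0.10/yr, post-switch hazard 0.30/yr and 5 years, all assumed.

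| n_on, n_off | Ignored | Event |
|---|---|---|
| 0.01, 0.01 | 1.12 | 0.13/0.13 = 1.00 |
| 0.01, 0.05 | 1.20 | 0.17/0.13 = 1.31 |
| 0, 0.05 | 1.09 | 0.17/0.12 = 1.42 |
| 0.01, 0.10 | 1.28 | 0.22/0.13 = 1.69 |

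It returns 1.00 only when such therapy is equally frequent on and off lenalidomide.

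**6. Direct switches.** Take the first row of step 5. Person-years per patient on lenalidomide are (1 − e^(−0.23×5))/0.23 = 2.971. Discontinued and before non-protocol therapy they are (1 − e^(−0.13×5))/0.13 − 2.971 = 0.705. Direct switches number 0.01 × 2.971 = 0.0297. If each is recorded as a stop 7 days before the new therapy, the discontinued rate is (0.13 × 0.705 + 0.0297)/(0.705 + 0.0297 × 7/365) ≈ 0.172. The on-lenalidomide rate is then 0.12, and the ratio 1.43 (1.44 by simulation) instead of 1.00. The coding of dates alone can move the result.

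**The case against.** The strongest reply is that the two-component sentence is shorthand. The model is introduced as an analysis of PFS, Exhibit 07LT-4B changes only the time origin, and SAP 1.2.1 uses similar shorthand for the primary endpoint: "Patients are considered a failure of the primary endpoint if they die or suffer from disease progression". The same phrase in the EFS model would, if literal, remove second primary malignancy from EFS, which suggests carried-over wording. This stands as far as intent goes: a reader might infer that the SAP deliberately adopted a second PFS definition, and the documents do not show that. But SAP 1.2.1 adds non-protocol therapy in its next sentence and the model paragraph never does. Shorthand in the sentence that defines a model's outcome still needs correcting.

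It can also be said that remaining at risk is an inference. That is fair, since no sentence says so for this model; it follows from the literal outcome and the general censoring rule.

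A reader might further infer that the omission necessarily biases the result against stopping, and that counting non-protocol therapy would restore an unbiased ratio. Neither is supported. The shift goes below 1 if the next regimen lowers the hazard, vanishes if it leaves the hazard unchanged, and the event-counted ratio exceeds 1 whenever such therapy more often follows stopping.

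Finally, the stakes are modest. The model is non-randomized and already caveated, and Exhibit 07LT-4B differs from Exhibits 07LT-3 and 07LT-4A in population and time origin anyway. That stands.

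**Conclusion.** The point holds as an unexplained mismatch between the stated outcome of this model and the plan's definition of PFS. Followed literally, the sentence yields a discontinuation hazard ratio for a different endpoint, one that includes person-time on the next regimen.

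The size cannot be determined from the documents. With no true effect of stopping on progression or death, the section-4 scenarios give 0.82 to 0.93 if the next regimen halves the hazard, 1.00 if it does not change it, and 1.11 to 1.30 if it doubles it. On the plan's own PFS events the same scenarios give 1.19 to 2.56. That is a property of the composite when non-protocol therapy follows stopping, not evidence that stopping causes progression. All switching, stopping and post-switch rates are assumptions.

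The primary log-rank test and the Cox model from randomization are unaffected. The correction is worth making because the ambiguity is easily removed, not because a particular bias has been shown.

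**What to change.** - In SAP 4.1 and the Exhibit 07LT-4B notes, set the outcome to time from initiation of maintenance lenalidomide to the earliest of progression, initiation of non-protocol anti-myeloma therapy, or death, using the primary PFS event variable.
- State that when lenalidomide is stopped in order to start non-protocol therapy, the event is attributed to the covariate state before the switch.
- Add a version that censors at non-protocol therapy, labelled as a sensitivity analysis. SAP 2.8 currently says none is planned, so amend that sentence and record the change in SAP 2.8.1.
- Extend the interpretation caveat to say that the event-counted ratio can exceed 1 simply because new therapy tends to follow stopping.
- Correct the EFS model from lenalidomide initiation (SAP 4.3, Supplemental Exhibit 07LT-6C) in the same way: restore second primary malignancy, and state how non-protocol therapy is handled, since Exhibit 07LT-6 groups it with progression while the EFS text in SAP 4.2 does not list it.

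The cost is a few sentences and one extra model run. The PFS event variable already exists and no new data are needed.
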